28MAY2014

NCT02416934

Unique Protocol ID: 1405296745

Brief Title: Dysphagia Following Anterior Cervical Spine Surgery; Steroid vs Saline (DysDexVSSal)

Title: The Effects of Perioperative Steroids on Dysphagia Following Anterior Cervical Spine Surgery: A Randomized, Prospective, Double-Blind Study

The Effects of Perioperative Steroids on Dysphagia Following Anterior Cervical Spine Surgery: A Randomized, Prospective, Double-Blind Study

This prospective, randomized, double blind, controlled study evaluates the effect of perioperative IV steroids versus saline on swallowing after anterior cervical spine surgery. The specific aim of this study is to determine if perioperative steroids can positively influence post-operative swallowing following anterior cervical surgery.

Literature Review

Anterior approaches to the cervical spine were developed in the late 1950s and have been a mainstay of operative treatment for cervical disorders. The most common etiology of cervical spine problems requiring surgery is degenerative in nature; however, traumatic, neoplastic, infectious, and deformity-based conditions that require surgery are often approached anteriorly as well. The common types of procedures include anterior cervical discectomy and fusion (ACDF) at one or more levels, anterior cervical corpectomy and strut grafting at one or more levels, hybrid reconstruction following corpectomy plus ACDF, and more recently, total disc arthroplasty. All of these procedures utilize the same operative dissection to expose the anterior cervical spine. They also all require retraction of the esophagus often for several hours in the more complex cases.

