Dysphagia is the term for symptomatic swallowing difficulties in patients. Swallowing is known to be a complex neuromuscular function with innervation from the pharyngeal plexus, the ansacervicalis, and cranial nerves IX, X, and XII. Virtually all patients will have some swallowing difficulty immediately after an anterior cervical spine procedure (1). The primary cause of this dysphagia is not believed to be denervation from the surgical approach but rather edema and late fibrosis in the esophageal tissue from the pressure of retractors (2,3). This has been shown histologically in a sheep study done by Cavusoglu et al (4). Other factors contributing to postoperative dysphagia include the presence of an anterior plate, the number of operative levels, higher levels of the cervical spine (such as C3-C4), duration of surgery, hematoma, and female gender (5-8).

Despite the anterior approach for cervical surgery having been popular for decades, it is only in the last several years that better studies have clarified the problem. In 2002, Bazaz et al. documented higher percentages of dysphagia months after surgery than had previously been known (9). These investigators obtained patient-reported symptoms at various time points up to one year following anterior cervical surgery. They developed a scale of none, mild, moderate, and severe symptoms of dysphagia and reported on 249 patients. The incidence of symptomatic swallowing difficulty was a surprising 50% at one month, 32% at two months, 18% at six months, and 12.5% at 12 months. Moderate to severe symptoms were still noted in 4.8% of patients six months post-operatively. Similarly, Riley et al. published on a large Cervical Spine Research Society cohort of 534 patients. Their data also showed a substantial percentage of symptoms three months post-operatively (29%). Six percent of patients still had some dysphagia 24 months post-operatively (10).

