This investigation is a prospective, randomized, double-blind, controlled trial testing peri-operative steroids versus saline and the effect on swallowing after anterior cervical spine surgery. Persons between the ages of 18 and 80 undergoing anterior cervical decompression and stabilization procedures for degenerative conditions are eligible for the study. This would include persons undergoing anterior cervical discectomy and fusion (ACDF), hybrid constructs, corpectomy(ies), and disc arthroplasty. Persons excluded from the study include those with major trauma, neoplastic, or infectious conditions requiring surgery. Also excluded are persons undergoing anterior-posterior operations, those with a history of previous anterior cervical spine surgery, any one requiring a halo vest, persons on chronic steroids, and persons remaining intubated postoperatively.

Swallowing symptoms will be measured using the patient reported Bazaz scale and the Dysphagia Short Questionnaire. Swallowing data will be obtained pre-operatively, one day and two days post-operatively and then one week, two weeks, four weeks, three months, six months, and one year post-operatively. Other data to be collected for analysis includes patient comorbidities, levels and type of surgery, intra-operative fluids, estimated blood loss, type of retractors, type of brace if any, length of stay, and other surgically related complications. Patient clinical outcomes will be captured using our web-based progress reports.

Participants in this study will complete the QoL-12, Neck Disability Index, and Visual Analog Scale questionnaires electronically pre-operatively and at one month, three months, six months, and one-year post-operative time points. This outcome data will help us analyze the swallowing function or symptoms with the overall clinical course of the participants enrolled in this study.

Inclusion Criteria:

- Elective anterior approach to subaxial cervical spine (C3 - T1)
- Ages 18-80

Exclusion Criteria

- Traumatic or tumor etiologies
- undergoing anterior-posterior operations
- neoplastic, or infectious conditions requiring surgery
- a history of previous anterior cervical spine surgery
- any patient requiring a halo vest
- patients on chronic steroids
- patients remaining intubated post-operatively (please see more under risks below)
- less than 18 years of age
- pregnant women
- no phone

Procedures

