Power and sample size calculations are based on the presence or absence of dysphasia at 2-weeks. Based on a literature review we postulated that 50% of the subjects in the control arm would experience mild, moderate or severe dysphasia. If that figure can be improved to the point where just 20% of the subjects are similarly affected, then that, in our opinion, would represent clinical success. Under the above scenario, 32 subjects in each arm would give us 81% power to reject the null hypothesis. We plan to analyze the data in two ways. First, we will look at the time-to-event where the event is "no dysphasia" in a discrete time survival model. Second, we will use a repeated measures ordinal categorical model to assess the effect of steroid/control in a generalized linear model. We have an electronic database that we will use to track patient outcomes. If subjects are unable to return to clinic, they will be able to complete the database questionnaires online. Our clinical research coordinator will also be able to contact subjects via phone to complete the Bazaz scale and Dysphagia Short Questionnaire.

Potential Risks/Discomforts/Privacy

Completion of the Bazaz scale and Dysphagia Short Questionnaire may cause some discomfort. The only expected side effect, in the group receiving steroids, would be possible elevation of serum glucose levels in diabetic subjects. The serum glucose levels in diabetic subjects will be monitored postoperatively with routine postoperative laboratory testing. All other procedures are standard of care.

Potential subjects will be recruited/consented for the study in private rooms at the Physician Office Center (POC) when they come for their History and Physical visit prior to surgery. All HIPAA safeguards are in place at the POC. Subjects will not be contacted outside of what is necessary for the research study.

Potential Benefits

To Subject: The group randomized to steroid administration may experience less or no dysphasia two weeks after the surgery.

To Society: The benefit to society will be publishing the results of the study regardless of whether we see improvement in dysphasia after administration of steroids or no improvement. Other surgeons performing this type of surgery will benefit knowing our results.

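### The 2-week endpoint and the survival event ignore the pre-operative dysphagia grade, so a prior complaint that persists unchanged is scored as post-operative dysphagia

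*Protocol*

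**What the plan says.** The opening paragraph of the protocol gives the aim: to "determine if perioperative steroids can positively influence post-operative swallowing following anterior cervical surgery". The Literature Review attributes the problem mainly to "edema and late fibrosis in the esophageal tissue from the pressure of retractors".

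Under Research Design, the narrative exclusions begin with major trauma, tumour and infection and continue: "Also excluded are persons undergoing anterior-posterior operations, those with a history of previous anterior cervical spine surgery, any one requiring a halo vest", then chronic steroid use and remaining intubated. The bulleted lists add pregnancy and having no phone. Neither the narrative nor the lists mention existing swallowing difficulty.

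The same section says "Swallowing data will be obtained pre-operatively, one day and two days post-operatively", followed by six later visits up to one year. Procedures and Consent Procedures repeat that the Bazaz scale and the Dysphagia Short Questionnaire are given before surgery.

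Data Analysis opens with "Power and sample size calculations are based on the presence or absence of dysphasia at 2-weeks". The planning rate is "50% of the subjects in the control arm would experience mild, moderate or severe dysphasia", against 20% under steroid, with 32 per arm and 81% power. For the analysis it says "First, we will look at the time-to-event where the event is" the absence of dysphagia, in a discrete-time survival model. The second analysis is a repeated-measures ordinal model. The protocol states no use for the pre-operative score in eligibility, in either definition or in either model.

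**The concern.** Take a patient with mild symptoms before surgery and mild symptoms at 2 weeks. Swallowing has not deteriorated, yet this patient counts as dysphagic in the sizing endpoint. For as long as the complaint stays mild, the patient does not reach the survival event either. If enough patients are like this, they raise the dysphagia rate in both arms for a reason unrelated to the operation, and the difference between the arms shrinks. The result then mixes two questions: who has any swallowing complaint, and who has one because of surgery.

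Adjusting for the pre-operative score as a covariate would help precision but would not change what counts as an event. The event definition is written into the protocol, so it is not something merely left to an analysis plan that is not shown.

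**Working it through.** **Inputs.** From Data Analysis: 50% (control), 20% (steroid), n = 32 per arm, stated power 81%. The protocol gives neither the significance level nor the sidedness, so 5% is assumed and both one-sided and two-sided results are shown. The share b of patients with pre-operative dysphagia is not given and is varied.

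**Formula (pooled z test).** Power = Φ{ [ (p1 − p2) − z·√(2p̄(1 − p̄)/n) ] / √( [p1(1 − p1) + p2(1 − p2)]/n ) }, where p̄ is the mean of p1 and p2.

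**Step 1: the protocol's own figure.** With 0.50 vs 0.20, p̄ = 0.35. The null standard error is √(2 × 0.35 × 0.65/32) = 0.1192, and the alternative standard error is √((0.25 + 0.16)/32) = 0.1132.
- One-sided: (0.30 − 1.645 × 0.1192)/0.1132 = 0.918, power 82.1%.
- Two-sided: (0.30 − 1.960 × 0.1192)/0.1132 = 0.586, power 72.1%.

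Only the one-sided test comes near 81%. That gap is a separate matter and is not counted here. What matters below is the fall within each column.

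**Step 2: full persistence.** Assume 50% vs 20% holds in patients free of dysphagia before surgery, and that every prior case is still symptomatic at 2 weeks. Then p1 = b + (1 − b) × 0.5 and p2 = b + (1 − b) × 0.2, so the difference is 30 × (1 − b) points.

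| b | Control vs steroid | Difference (points) | Power, one-sided | Power, two-sided |
|---|---|---|---|---|
| 0 | 50% vs 20% | 30 | 82% | 72% |
| 5% | 52.5% vs 24% | 28.5 | 77% | 66% |
| 10% | 55% vs 28% | 27 | 72% | 60% |
| 15% | 57.5% vs 32% | 25.5 | 66% | 54% |
| 20% | 60% vs 36% | 24 | 61% | 48% |

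**Step 3: weaker assumptions, b = 10%.**
- Half of the prior cases persist whatever is given and half behave like the rest: 0.05 + 0.95 × 0.5 = 52.5% vs 0.05 + 0.95 × 0.2 = 24%. Two-sided power is 66%.
- Prior cases can respond, with an assumed 80% vs 50% still symptomatic: 0.1 × 0.8 + 0.9 × 0.5 = 53% vs 0.1 × 0.5 + 0.9 × 0.2 = 23%. Two-sided power is 70.5%, against 72.1% at b = 0. At b = 20% it is 69.3%.
- The stated 50% and 20% already include prior cases: the rates stay at 50% vs 20% and nothing is lost.

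**Step 4: what redefinition does, b = 10%, two-sided.** Count prior cases only if they worsen.
- If none worsen: 0.9 × 0.5 = 45% vs 0.9 × 0.2 = 18%, power 64.9%.
- If an assumed 25% vs 10% worsen: 0.1 × 0.25 + 0.45 = 47.5% vs 0.1 × 0.10 + 0.18 = 19%, power 68.5%.

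Against 59.5% under full persistence, the gain is about 5 to 9 points. Against 70.5% in the responding case, the 25% vs 10% assumption costs about 2 points.

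**The case against.** The best defence is that the aim is worded as post-operative swallowing, and Potential Benefits speaks of less or no dysphagia at two weeks. An absolute state fits that wording, so the protocol does not contradict itself. The retractor mechanism is background and does not define an endpoint. This stands. The point concerns how well the event fits the question, not an inconsistency.

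A reader might infer that patients with prior dysphagia are certain failures whatever the steroid does. The documents do not support that. Nothing says the prior complaint is permanent. Such a patient can reach freedom from dysphagia at any of eight post-operative visits, and one who never does is censored in the survival model. Censoring does not restore the lost contrast, but it is not a fixed failure.

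A reader might also infer that the trial is biased, or that chance imbalance in prior cases adds a further error. Randomisation balances such cases on average, and chance imbalance is already part of the binomial variance in the power figures.

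A harsher calculation is possible: let the 50% include prior cases while the steroid's relative reduction reaches only the rest. At b = 10% that gives 50% vs 0.10 + 0.40 × 0.4 = 26%, and two-sided power of 51%. The text does not support this reading, because it states the 20%, like the 50%, for all subjects. The same wording counts against treating Step 2 as the expected loss.

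Finally, the ordinal model uses graded severity and can register worsening and partial recovery. An unseen analysis plan may adjust for the pre-operative score. Both soften the point, but neither alters the sizing endpoint or the first analysis.

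**Conclusion.** The point holds in a limited form. Prior dysphagia is no bar to entry, the pre-operative grade is collected, and the sizing endpoint and survival event both disregard it. An unchanged prior complaint is therefore scored as post-operative dysphagia in either arm. The consequence is possible loss of power and a less clear answer about surgery-related swallowing, not bias between the arms.

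The size cannot be fixed from the documents. At b = 10%, the loss is about 10 points one-sided (82% to 72%) or 12 to 13 points two-sided (72.1% to 59.5%). This needs both assumptions: that 50% vs 20% applies to patients free of dysphagia before surgery, and that every prior case persists. The loss is under 2 points two-sided if such patients respond as assumed in Step 3, and nil if both stated rates already include them. The change is worth making because the data are already collected and nothing alters for a patient graded as having no symptoms before surgery.

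**What to change.** In Data Analysis:
- Define the 2-week endpoint as dysphagia that is new or worse than the pre-operative Bazaz grade.
- Define the survival event as return to the pre-operative grade or better.
- Include the pre-operative grade as a covariate in both models.
- Report the absolute any-dysphagia version alongside as a sensitivity analysis.
- Note that the 50% vs 20% assumption was stated for any dysphagia and say how it carries over to the redefined endpoint.

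**Cost.** Revised wording, one derived variable and a sentence on the sizing assumption. No new data, visits or patients are needed. Two downsides should be stated openly: a patient who is back at a symptomatic pre-operative level counts as recovered, and a patient graded severe before surgery cannot worsen. The absolute version covers both and keeps the results comparable with published any-dysphagia rates. If prior cases do respond to treatment, the new definition may cost about 2 points of power (Step 4).

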Persons who have chosen to undergo anterior cervical spine surgery will be seen at the clinic for a pre-operative visit. The surgeons on the protocol will discuss the study and the subjects will be given the opportunity to participate. If the subjects agree to participate, a consent form will be administered by a member of the research team. The Bazaz and Dysphagia Short Questionnaire will be administered to subjects at this visit prior to surgery and again at Day 1, Day 2, 1 week, 2 weeks, 1 month, 3 months, 6 months, and 12 months after surgery. If the subject does not come for a clinic visit at the follow up times, he/she will be called to answer the questions on the surveys. The windows-of-time in which subjects may be called after discharge include: for follow up for week 1 and week 2, two days before or after the actual day of 1 or 2 weeks; for week 4, three days before or after the actual day of 4 weeks; for 3 months and 6 months, a week before or after the actual date of 3 or 6 months; for 1 year, 2 weeks before or after the actual date of 1 year. Subjects will be randomized to either the steroid administration group or the saline administration group. Subjects randomized to the experimental (steroid) group will receive 0.3 mg/kg of intravenous dexamethasone within one hour of the incision, then 0.15 mg/kg every eight hours (window of time 45 minutes on both ends of the eight hour time, e.g. if the time is 8 pm, the dose could be given from 7:15 pm through 8:45 pm) for two doses. This dosage is approximately 20 mg, 10 mg, and 10 mg of dexamethasone. Subjects in the control (saline) group will receive a similar volume of saline on the same schedule for three doses. This is a double-blind trial; the surgeon (and anesthesiologist) and the subject will not know what group assignment the subject has received. The in-patient pharmacy will generate IV bags that are labeled for the study but that are blinded as to medication/saline labels. Randomization will be performed by the satellite pharmacist outside of the operating room. This person will also supply the study drug.

Sample Size

70

Sample Size justification

Our power analysis indicates 64 subjects with 32 in each arm is enough to give us 81% power to reject the null hypothesis. We are adding an additional 10% to that number as we expect to have a loss to follow up of approximately 10%.

Data Analysis

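### Does the 50% control rate used to size the trial at 2 weeks belong to a different visit?

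*Protocol*

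**What the plan says.** The Data Analysis section names the visit used for sizing: "Power and sample size calculations are based on the presence or absence of dysphasia at 2-weeks". It then sets the control rate: "Based on a literature review we postulated that 50% of the subjects in the control arm would experience mild, moderate or severe dysphasia". The target follows: "If that figure can be improved to the point where just 20% of the subjects are similarly affected". With 32 evaluable subjects per arm the protocol reports 81% power; alpha and sidedness are not given.

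The Literature Review reports one series with rates over time: "The incidence of symptomatic swallowing difficulty was a surprising 50% at one month, 32% at two months". Of that series it says: "They developed a scale of none, mild, moderate, and severe symptoms of dysphagia and reported on 249 patients". For the period before one month it says only this, from a different reference: "Virtually all patients will have some swallowing difficulty immediately after an anterior cervical spine procedure".

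The Potential Benefits section also names 2 weeks: "The group randomized to steroid administration may experience less or no dysphasia two weeks after the surgery". The follow-up schedule lists the 2-week visit and the 4-week (one-month) visit separately.

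**The concern.** The planning rate and the planning visit do not visibly belong together. The review's single 50% is a one-month figure, graded none to severe just like the planning definition, so it is natural to suspect that it was carried back to 2 weeks. The choice of 2 weeks is not a typing slip, since the benefit statement repeats it. The protocol's own account runs from nearly everyone affected just after surgery, to 50% at one month, to 32% at two months. A steady decline along that path would put 2 weeks at or above 50%.

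At stake would be the meaning of the power figure. A fall to 20% is a 30-point benefit if control is 50%, a 40-point benefit if it is 60% and a 50-point benefit if it is 70%. A reader could then not tell which benefit 32 per arm was meant to detect, or whether 81% applies at the visit named.

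**Working it through.** **Inputs.** From the protocol: 32 per arm, 50% against 20% at 2 weeks, stated power 81%; review rates of 50% at one month and 32% at two months. Assumed, because not stated: alpha 5%, shown one-sided with two-sided in brackets, and a pooled normal-approximation test of two proportions.

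**Formula.** With mean rate p̄ = (p1 + p2)/2,

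power = Φ{ [ |p1 − p2| − z·√(2p̄(1 − p̄)/n) ] / √([p1(1 − p1) + p2(1 − p2)]/n) }

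with z = 1.645 one-sided and 1.960 two-sided.

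**Reproducing the stated figure.** For 50% against 20%, p̄ = 0.35. The null standard error is √(0.455/32) = 0.1192 and the alternative one is √(0.41/32) = 0.1132.
- One-sided: (0.30 − 1.645 × 0.1192)/0.1132 = 0.917, so power is 82.1%, close to the stated 81%.
- Two-sided: (0.30 − 1.960 × 0.1192)/0.1132 = 0.586, so power is 72.1%.

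**How far above 50% might 2 weeks be?** The protocol gives no figure, so any value is an assumption. Take day 14 and a month of 30.4 days.
- Extrapolating back from the one- and two-month rates: linear 0.50 + 0.18 × (16.4/30.4) = 0.597; on the logit scale 0.600; exponential 0.50 × (0.50/0.32)^(16.4/30.4) = 0.636.
- Interpolating between 100% at day 0 and 50% at one month: exponential 0.50^(14/30.4) = 0.727; linear 1 − 0.50 × (14/30.4) = 0.770.

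The first group lies outside the data it uses. The second joins statements from two different sources. A steep early fall that then flattens would leave 2 weeks close to 50%.

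**Power at 32 per arm if the control rate is higher**, in %, one-sided (two-sided):

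| Control rate | 20% target kept | 30 points kept | Risk ratio 0.40 kept | Odds ratio 0.25 kept |
|---|---|---|---|---|
| 50% | 82.1 (72.1) | 82.1 (72.1) | 82.1 (72.1) | 82.1 (72.1) |
| 55% | 90.9 (84.1) | 80.1 (69.6) | 87.2 (78.8) | 84.1 (74.7) |
| 60% | 96.2 (92.4) | 78.9 (68.2) | 91.4 (84.8) | 85.4 (76.4) |
| 65% | 98.8 (97.0) | 78.6 (67.8) | 94.7 (89.9) | 86.0 (77.3) |
| 70% | 99.7 (99.1) | 78.9 (68.2) | 97.1 (93.9) | 85.9 (77.1) |
| 80% | >99.9 (>99.9) | 82.1 (72.1) | 99.4 (98.5) | 82.1 (72.1) |

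The risk ratio and odds ratio are those implied by 50% against 20%: 0.20/0.50 = 0.40 and (0.20/0.80)/(0.50/0.50) = 0.25.

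Only the fixed 30-point reading loses power. Its worst case is 65% against 35%: 82.1 − 78.6 = 3.5 points one-sided and 72.1 − 67.8 = 4.3 points two-sided.

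**Where it would matter.** A control rate below 50% would hurt: at 40% against 20%, power is 54.1% (41.3%). The review gives no reason to expect that at 2 weeks. At the other extreme, a 90% control rate with the odds ratio held at 0.25 gives 66.7% (54.2%), but that rate lies beyond every interpolated value above.

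**The case for a change.** The best case for acting is that the protocol rests its 50% on the literature, the only literature it reports supports 50% at another visit, and the remedy is to reword one paragraph. At a 60% control rate the one power figure could stand for about 96% with the 20% target or about 79% with a 30-point difference (92% or 68% two-sided), and a protocol should say which.

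Part of this stands. The rate is uncited for the visit it describes, and a reference or a short range of control rates would have made the paragraph better. The rest does not carry. The protocol calls 50% a postulate and does not attribute it to the one-month figure. Its reference list contains other papers on the incidence of dysphagia whose rates the review does not report, so a 2-week source cannot be ruled out. The two readings are also not equally open: the protocol words its target as 20% of subjects affected, and the 30-point difference is only the subtraction implied at 50%. Moving the sizing calculation to the 4-week visit, where the review does support 50%, would take it away from the visit that the benefit statement names, merely to suit a literature figure.

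**Conclusion.** No change is needed. The text shows an unsupported planning assumption, not a demonstrated error. If the assumption is off in the direction the review suggests, the protocol's own 20% target becomes easier to detect statistically, though it asks more of the treatment. The loss under a fixed 30-point reading is at most 3.5 points one-sided or 4.3 two-sided, for control rates of 50% to 80%. The two planned analyses, a discrete-time survival model and a repeated-measures ordinal model, do not use the postulated rate, so a citation or rewording would leave the sample size, the analyses and the conclusions as they are.

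This rests on an assumed 5% alpha, the pooled test and 32 evaluable subjects per arm. It covers the control rate only and does not endorse 81% as adequate power. That figure is approached one-sided (82.1%) but not two-sided (72.1%), and the missing alpha and sidedness are a separate matter.

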Steroids have long been used clinically for their physiologic effect of decreasing soft tissue edema. This effect has been utilized commonly in patients with spinal cord injury, cerebral swelling, and various pulmonary conditions. Some studies suggest a decrease in upper airway edema following cervical spine surgery, (11) though a randomized controlled trial done by Emery et al. found no benefit from steroids in the multi-level corpectomy patient population (12). Lee et al did a randomized study regarding intraoperative steroid soaked collagen sponges and their effect on prevertebral soft tissue swelling (13). The measurable soft tissue edema was decreased in the early time periods in the steroid group, and lower VAS (visual analog scale) scores regarding odynophagia were documented in the steroid group as well. Our study will use intravenous steroids and use two established dysphagia questionnaires for a more focused, in depth investigation of post-operative swallowing symptoms.

Steroids can cause hyperglycemia in predisposed patients such as diabetics and chronic use can suppress the immune system. High doses for longer periods of time can also result in avascular necrosis of the femoral head. In very short treatment periods such as a few days, the safety profile for steroid use is extremely high and indeed remains a common treatment option in spine patients as well as in many other disciplines. If steroids are beneficial in this clinical setting, it could lead to greater patient satisfaction, decreased hospital length of stay, and perhaps avoid permanent symptoms of dysphagia. If steroids are of no benefit than decreased peri-operative use could result in cost savings and avoid potential complications of the drug.

1. Riley LH 3rd, Vaccaro AR, Dettori JR, et al. Postoperative dysphagia in anterior cervical spine surgery. *Spine* 2010;35(9 Suppl):S76-85.

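### Does a survival model with absence of dysphagia as its event wrongly count a single early symptom-free report as lasting recovery?

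*Protocol*

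**What the plan says.** The Data Analysis section plans two analyses and ranks neither. For the first, "we will look at the time-to-event where the event is" the absence of dysphagia, in a discrete time survival model. The next sentence reads: "Second, we will use a repeated measures ordinal categorical model to assess the effect of steroid/control in a generalized linear model". Nothing says whether the survival event is the first symptom-free report or sustained absence, whether it needs confirmation, or how a return of symptoms is handled.

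Under Procedures the swallowing questionnaires are given before surgery and "again at Day 1, Day 2, 1 week, 2 weeks, 1 month, 3 months, 6 months, and 12 months after surgery", which makes eight postoperative time points. The sample size rests on dysphagia status at 2 weeks (50% against 20%, 32 per arm, 81% power), not on the survival model.

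**The concern.** A standard discrete-time survival model fits an event that happens once. A subject counts as at risk until the first visit with the event, and later visits contribute nothing. Swallowing status is not of that kind: a patient can report no difficulty on Day 2 and difficulty at week 1.

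Three features of the protocol make this look serious. The Literature Review attributes dysphagia to "edema and late fibrosis in the esophageal tissue from the pressure of retractors", so an early and a late phase are both conceivable. After the first dose the steroid is given "then 0.15 mg/kg every eight hours" for two doses, so exposure spans about 16 hours and the first outcome visits follow directly. The protocol also hopes that treatment will "perhaps avoid permanent symptoms of dysphagia", which a first-event analysis cannot show.

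At stake is a positive result from the analysis listed first, driven by brief relief of oedema, when the arms no longer differ at 2 weeks or later.

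**Working it through.** **The plan's own figure.** With 32 per arm and 50% against 20%, the pooled proportion is 0.35. The null standard error is √(2 × 0.35 × 0.65 / 32) = 0.1192 and the alternative standard error is √((0.25 + 0.16) / 32) = 0.1132. One-sided at 0.05: (0.30 − 1.645 × 0.1192) / 0.1132 = 0.92, power 82.1%. Two-sided at 0.05: (0.30 − 1.960 × 0.1192) / 0.1132 = 0.59, power 72.1%. The stated 81% is thus close to the one-sided value; the protocol does not give the significance level. The figure concerns 2-week status and does not depend on how the survival event is defined.

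**How far first-event coding and true status can differ.** All inputs here are assumed, because the protocol gives no relapse rate. Let q be the proportion symptom-free by Day 2 (10% control, 30% steroid), h = 0.25 the recovery probability at each of weeks 1 and 2 in both arms, and r the probability that someone symptom-free early relapses at week 1.

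- Recovered by 2 weeks, first-event coding: 1 − (1 − q)(1 − h)². The difference between arms is 0.20 × 0.5625 = 0.1125, whatever r is.
- Symptom-free at 2 weeks: q[(1 − r) + rh] + (1 − q)[1 − (1 − h)²]. The difference is 0.20 × (0.5625 − 0.75r).

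| r | True difference at 2 weeks | Rejection, first event | Rejection, sustained event |
|---|---|---|---|
| 0 | 11.25 points | 19% | 19% |
| 0.25 | 7.5 points | 19% | 11% |
| 0.50 | 3.75 points | 18% | 7% |
| 0.75 | 0 points | 18% | 5% |

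The rejection columns come from simulation (32 per arm, eight visits, discrete log-rank test, two-sided 0.05, 2,000 trials per row). With no relapse the two definitions agree. They part only as r grows.

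**How much depends on the assumed correlation.** A second simulation took control dysphagia rates of 95, 90, 70, 50, 50, 29, 18 and 12.5% at the eight visits and an odds ratio of 0.25. That is the planned effect: odds of 1 at 50% become 0.25, and 0.25 / 1.25 = 20%. The effect was applied on Days 1 and 2 only.

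| Latent correlation between visits | Relapse after a first symptom-free report | Rejection, first event | Rejection if early dysphagia is lower (80, 75, 60%) |
|---|---|---|---|
| 0.5 | 49% | 12% | 38% |
| 0.8 | 26% | 7% | 19% |
| 0.9 | 15% | 7% | 14% |
| 0.95 | 8% | 7% | 10% |

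**Validity under no effect.** With no treatment effect at any visit, first-event coding rejects in about 4 to 6% of trials. The test holds its level.

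**Price of a confirmed event.** Suppose the event must be confirmed at the next scheduled visit. If the effect lasts through 4 weeks, which includes the 2-week time point, power falls by about 10 to 21 points: for example from 82% to 62%, or from 61% to 41%. If the effect persists at all visits, power is about 90% under either definition.

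**The case for a change.** The strongest case for a change is that the protocol itself selects both model and event, so this is a stated choice and not merely an omission. Default software coding would use the first symptom-free report. The two analyses have no declared order, so a positive survival result could be presented as benefit while the ordinal model shows nothing. Two simulations with different set-ups agree on the direction, and a clarification costs one sentence.

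Part of this stands. Under default coding, relapse is invisible to that one analysis, and a first-event result should be read as time to first symptom-free report, not as lasting recovery.

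The rest is weaker. The text never says first, terminal or lasting; that reading is inferred from the default. The ordinal model in the next sentence can use the status at every visit, so recurrence and late onset do enter the planned analyses. The protocol gives no individual relapse rate. It cites only group incidence, which falls steadily from 50% at one month to 12.5% at 12 months, and late fibrosis could as well explain persistence as return. It also states that "Virtually all patients will have some swallowing difficulty immediately after an anterior cervical spine procedure", which points to few Day 1 events. Finally, the simulated drug does work on Days 1 and 2. Rejecting the null there is a correct finding of a short benefit, and earlier relief bears on the stated aim and on the hoped-for shorter hospital stay.

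**Conclusion.** The concern does not call for a change. First against sustained absence is a detail that an analyst or a SAP settles sensibly, and neither option is wrong. First-event coding keeps its type I error (about 4 to 6%). It responds to a real early effect in about 7 to 38% of trials, depending on assumed rates and correlations that the protocol does not supply. A confirmed event answers a different question and loses about 10 to 21 points of power when the effect is temporary but still present at 2 weeks. Because late visits are 3 to 6 months apart, confirmation would also mean different things along the schedule.

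The sample size is unaffected, and the ordinal repeated measures model covers what the survival model cannot see. Ranking a 2-week comparison first is a separate question about the primary endpoint and would not alter how relapse is coded. The proportion whose symptoms return can be described from data already collected. The conclusion rests on the ordinal model being fitted to all visits as planned, and on a first-event result being described as what it is.
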